5.3 Concomitant therapy

- All patients should be maintained on the same medications throughout the study period, as medically feasible;
- The investigator should instruct the patient to notify the study staff about any new medications he/she takes after the start of the study drug. All medications (other than study drug) and significant non-drug therapies (including physical therapy and blood transfusions) administered after the patient starts treatment with study drug must be recorded;
- Administration of pegfilgrastim or filgrastim following initiation of protocol therapy is at investigator's discretion for all patients;
- Administration of erythropoietin or darbopoietin is allowed;
- Other concurrent investigational drugs of any type are not allowed in the trial;
- Other concurrent anticancer agents (with the exception of somatostatin analogs) are not allowed in the trial;
- Patients must be instructed not to take any additional medications (including herbal supplements and over-the-counter products) during the trial without prior consultation with the investigator. All medications taken within 30 days of screening should be recorded. If concomitant therapy must be added or changed, the reason and name of the drug/therapy should be recorded;
- In general, the use of any concomitant medication/therapies deemed necessary for the care of the patient are allowed, including drugs given prophylactically (e.g. antiemetics or steroids), with the following exceptions:
- CYP3A Inhibitors/Inducers
 - Ibrutinib is metabolized primarily by CYP3A. Avoid co-administration with strong or moderate CYP3A inhibitors and consider alternative agents with less CYP3A inhibition.

- Strong inhibitors of CYP3A (eg, ketoconazole, indinavir, nelfinavir, ritonavir, saquinavir, clarithromycin, telithromycin, itraconazole, nefazadone, or cobicitstat) should be avoided
- If a strong CYP3A inhibitor (see Appendix A) must be used, ibrutinib will be reduced to 140 mg or withheld for the duration of inhibitor use.. Subjects will be monitored more closely for signs of ibrutinib toxicity (at the investigator's discretion). If a moderate CYP3A inhibitor (see Appendix A) must be used, ibrutinib will be reduced to 140 mg (for 840 mg/day dose, reduce to 280mg) for the duration of the inhibitor use. No dose adjustment is required in combination with mild inhibitors.
 - Grapefruit and Seville oranges should be avoided during ibrutinib treatment, as these contain moderate inhibitors of CYP3A (see Appendix A)
 - Co-administration of ibrutinib with strong CYP3A inducer, rifampin, in healthy subjects decrease ibrutinib plasma concentrations by approximately 10-fold. Avoid concomitant use of strong CYP3A inducers (eg, carbamazepine, rifampin, phenytoin, and St. John's Wort). Consider alternative agents with less CYP3A induction.
 - A list of common CYP3A inhibitors and inducers is provided in Appendix A. A comprehensive list of inhibitors, inducers, and substrates may be found at <http://medicine.iupui.edu/clinpharm/ddis/main-table/> This website is continually revised and should be checked frequently for updates.
- Anti-platelet Agents and Anticoagulants:
 - Warfarin or vitamin K antagonists should not be administered concomitantly with ibrutinib. Supplements such as fish oil and vitamin E preparations should be avoided. Use ibrutinib with caution in subjects requiring other anticoagulants or medications that inhibit platelet function. Subjects with congenital bleeding diathesis have not been studied. For guidance on ibrutinib and the use of anticoagulants during procedures/surgeries see Section 5.5.
 - Patients who need to be on anticoagulant therapy during treatment with ibrutinib should be treated with low molecular weight heparin as the preferred therapy. Patients who are on full dose anticoagulation therapy while being treated with ibrutinib and who experience concurrent grade 3 or 4 thrombocytopenia/bleeding despite single ibrutinib dose reduction will permanently discontinue ibrutinib treatment.
 - Subjects requiring the initiation of therapeutic anticoagulation therapy (eg, atrial fibrillation), consider the risks and benefits of continuing ibrutinib treatment. If therapeutic anticoagulation is clinically indicated, treatment with ibrutinib should be held and not be restarted until the subject is clinically stable and has no signs of bleeding. Subjects should be observed closely for signs and symptoms of bleeding. No dose reduction is required when study drug is restarted.

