Recent epidemiological data suggest a rising incidence of NETs and increased survival durations over time, but the long-term outcome of patients with advanced-stage disease still remains poor⁴⁻⁷. Although historically perceived as similar entities, it is increasingly clear that low- and intermediate-grade pNETs and carcinoid tumors have different biology and respond differently to therapeutic agents. Carcinoid tumors are relatively insensitive to conventional chemotherapy and have no established treatment other than somatostatin analogs (SSAs)⁸. Initially developed to palliate hormonal symptoms, SSAs such as octreotide and lanreotide have been also shown to slow tumor progression in patients with advanced carcinoid tumors. In fact, the randomized phase III PROMID trial evaluated octreotide long-acting repeatable (LAR) versus placebo in patients with metastatic midgut NETs and demonstrated a significant improvement in time-to-progression⁹. More recently, the CLARINET trial randomized patients with hormonally nonfunctioning gastroenteropancreatic NETs to receive depot-lanreotide versus placebo, also demonstrating a statistically significant improvement in progression-free survival (PFS)¹⁰. pNETs appear to be more sensitive to cytotoxic chemotherapy¹¹, however there are no placebo-controlled chemotherapy trials and the role of cytotoxic drugs remains controversial. Approved treatment agents for pNETs include everolimus and sunitinib. The mTOR inhibitor everolimus was recently found to significantly prolong PFS in patients with advanced pNETs¹². A randomized phase III trial of sunitinib, a multitargeted tyrosine kinase inhibitor, in pNETs demonstrated significant improvement in PFS from 5.5 months on the control arm to 11.4

months on the experimental arm¹³. Despite these encouraging results in terms of PFS prolongation, tumor regression is uncommon with targeted agents and no overall survival benefit has been demonstrated¹⁴.

Although impressive progress in the biotherapy field has been made over the last decade, no proven therapeutic options for patients progressing on initial therapy are currently available and response to second line therapies is poorly documented, as demonstrated by lack of recommendations from recent consensus statements⁵. Therefore, there is an urgent need for new and effective agents for both carcinoids and pNETs, and novel cellular and molecular targets needs to be exploited.

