4.4.1 Inclusion criteria

1. Locally unresectable or metastatic carcinoid or pNET;
2. Measureable disease by RECIST criteria;
3. Tumors must be histologically or cytologically proven and considered low or intermediate grade. Patients with high grade neuroendocrine carcinomas or small cell carcinomas are excluded from the study;
4. Evidence of progressive disease within 12 months of study entry;
5. Allowed prior therapies include:

- a) Surgery (major surgery at least more than four weeks prior to baseline assessment);
 - b) Locoregional therapy such as: chemoembolization, radio-embolization, radiofrequency ablation, radiotherapy as long as there is progressive measurable disease outside the area of locoregional therapy or there is progression in the previously treated areas;
 - c) Any number of previous lines of systemic therapy. Last treatment before enrollment must have occurred more than 4 weeks for chemotherapy, 6 weeks for antibodies or more than 5 half lives of prior TKIs or small molecules;
6. Prior or concurrent therapy with somatostatin analogs is permitted for patients with secretory NET;
 7. All patients with gastroenteropancreatic NETs must have progressed on (or are intolerant of) prior somatostatin analog;
 8. Patients with pancreatic NETs must have progressed on (or are intolerant of) either everolimus or sunitinib;
 9. Age \geq 18 years;
 10. ECOG performance status of 0-2;
 11. Life expectancy 12 weeks or more;
 12. Adequate bone marrow function as shown by: absolute neutrophil count \geq 1,000/mm³, Platelets \geq 100,000/mm³, Hb > 10 g/dl;
 13. Adequate liver function as shown by: serum bilirubin \leq 1.5 x ULN, and serum transaminases activity \leq 2.5 x ULN, with the exception of serum transaminases ($< 3 \times$ ULN) if the patient has liver metastases;
 14. Adequate renal function as shown by serum creatinine \leq 2 mg/dl;
 15. Women of childbearing potential must have a negative serum pregnancy test within 7 days of the administration of the first study treatment. Women must not be lactating. Both men and women of childbearing potential must be advised of the importance of using effective birth control measures during the course of the study. Childbearing potential for women and men is defined in section 4.4.3;

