4.4.2 Exclusion criteria

1. High grade NET or small cell neuroendocrine carcinoma;
2. Clinically apparent central nervous system metastases or carcinomatous meningitis;
3. Known positive test for human immunodeficiency virus (HIV), hepatitis B virus (HBV), or hepatitis C virus (HCV);
4. History of stroke or intracranial hemorrhage within 6 months prior to the first dose of study drug;
5. Clinically significant cardiovascular disease such as uncontrolled or symptomatic arrhythmias, congestive heart failure, or myocardial infarction within 6 months of screening, or any class III or IV cardiac disease as defined by the NYHA functional classification;
6. Requirement for anticoagulation with warfarin or similar vitamin K antagonists.

7. Requirement for treatment with a strong cytochrome P450 (CYP) 3A4/5 inhibitor. (See Appendix A)
8. Prior antitumor therapy within 2 weeks of enrollment (with the exception of somatostatin analogs);
9. No other active malignancy within 3 years of enrolment except adequately treated basal cell or squamous cell skin cancer, in situ cervical cancer, adequately treated stage I or II cancer from which the patient is currently in complete remission, or any other cancer from which the patient has been disease free for at least three years;
10. Any medical condition or organ system dysfunction which, in the investigator's opinion, could compromise the patient's safety, interfere with the absorption or metabolism of ibrutinib;
11. Known hypersensitivity to ibrutinib or any component of the ibrutinib formulation;
12. History of noncompliance to medical regimens or unwillingness to comply with the protocol.
13. Currently active, clinically significant hepatic impairment Child-Pugh class B or C according to the Child Pugh classification (see Appendix D)

Comment [AT2]: RESPONSE REQUIRED:

Please include the following exclusion criteria regarding hepatotoxicity.

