7.3 Confirmation Measurement/Duration of Response

Confirmation: To be assigned a status of PR or CR, changes in tumor measurements must be confirmed by repeat studies that should be performed no less than 4 weeks after the criteria for response are first met. In the case of SD, follow-up measurements must have met the SD criteria at least once after study entry at a minimum interval of 6 weeks. Progression of disease should be verified in cases where progression is equivocal. If repeat scans confirm PD, then progression should be declared using the date of the initial scan. If repeat scans do not confirm PD, then the subject is considered not to have progressive disease per RECIST 1.1.

Duration of Overall Response: The duration of overall response is measured from the time measurement criteria are met for CR/PR (whichever is first recorded) until the first date that recurrent or progressive disease is objectively documented (taking as reference for progressive disease the smallest measurements recorded since the treatment started).

The duration of overall complete response is measured from the time measurement criteria are first met for CR until the first date that recurrent disease is objectively documented.

Duration of Stable Disease: Stable disease is measured from the start of the treatment until the criteria for progression are met, taking as reference the smallest measurements recorded since the treatment started.

Progression Free Survival (PFS): PFS is defined as the time from the date of first study treatment to the date of the first documented disease progression or death due to any cause. If a patient has not progressed or died at the date of the analysis cut-off or when he/she receives any further anti-cancer therapy, PFS is censored at the time of the last tumor assessment before the cut-off or the anti-cancer therapy date.

Time to Treatment Failure: Time from administration of the initial dose of ibrutinib until study discontinuation for any reason (e.g. disease progression, toxicity, death, withdrawal of consent).

Biochemical marker response will be defined as $\geq 50\%$ reduction in tumor marker from baseline.

8. Statistical Considerations

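### Somatostatin analogs may be started or increased on study, but the biochemical-response definitions ignore such a change and the PFS censoring rule does not say whether it counts

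*Combined protocol and SAP*

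**What the plan says.** **On-study use.** Section 5.3 exempts analogs from the ban on anticancer agents: "Other concurrent anticancer agents (with the exception of somatostatin analogs) are not allowed in the trial". The general brake in the same section is: "All patients should be maintained on the same medications throughout the study period, as medically feasible". It also foresees changes: "If concomitant therapy must be added or changed, the reason and name of the drug/therapy should be recorded".

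**Entry.** Criterion 6 in 4.4.1 reads: "Prior or concurrent therapy with somatostatin analogs is permitted for patients with secretory NET". Criterion 7 reads: "All patients with gastroenteropancreatic NETs must have progressed on (or are intolerant of) prior somatostatin analog". Section 4.3 also admits lung and unknown-primary tumors, which criterion 7 does not name. Section 4.4.2 lifts the two-week washout for analogs, and no stable-dose period is asked for.

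**Activity.** Section 1.1 says analogs were first developed to relieve hormonal symptoms, and adds: "SSAs such as octreotide and lanreotide have been also shown to slow tumor progression in patients with advanced carcinoid tumors".

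**Endpoints.** Section 7.3 defines biochemical marker response as a reduction of at least 50% from baseline. Section 8.2 defines early biochemical response as a chromogranin A (CgA) reduction above 50%, or normalization, at the assessment three months after baseline. Neither mentions analog use. For PFS, 7.3 says that "when he/she receives any further anti-cancer therapy, PFS is censored at the time of the last tumor assessment". The PFS definition in 8.2 has no censoring rule, and 8.3 plans Kaplan-Meier estimation only.

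**The concern.** A symptomatic patient may have an analog added or increased during treatment. If the marker then falls, the definitions in 7.3 and 8.2 record a biochemical response, and with no control arm nothing separates the analog's share from ibrutinib's. Section 8.2 then relates early biochemical response to response rate and PFS, so the misattribution can carry into that exploratory analysis.

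For PFS the problem is one undefined term. Section 5.3 groups analogs with anticancer agents and at the same time permits them. Two analysts could therefore read the censoring rule differently for the same patient: one censors at the last scan before the analog change, the other keeps following. In cohorts of 30 and 21 a few such patients can move a median, and the choice could be made after the data are seen.

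**Working it through.** **1. The plan's own figures.** The only powered endpoint is response rate. The exact two-stage probability of success is the sum, over stage-1 responses x ≥ 1, of P(X1 = x) × P(stage-2 responses ≥ r − x).
- Carcinoid (15 then 30 patients, ≥1 then ≥4 responses): type I error 0.0582 at 5%, power 0.8002 at 18%. Stated: 6% and 80%.
- pNET (12 then 21 patients, ≥1 then ≥3 responses): type I error 0.0804 at 5%, power 0.8033 at 20%. Stated: 8% and 80%.

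These reproduce. No figure is stated for PFS or biochemical response, so there is none to reproduce there.

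**2. The rules side by side.**

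| Question | Marker response (7.3) | Early CgA response (8.2) | PFS (7.3) |
|---|---|---|---|
| Is there a rule after an analog start or increase? | None | None | Yes: censor at further anti-cancer therapy |
| Is it clear for analogs? | Every later value counts | The 3-month value counts | No: the term is not defined for analogs |
| Which changes matter? | Any before a later marker value | Only those before the 3-month assessment | Any before progression |

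**3. Illustration for biochemical response.** All inputs are assumed: true ibrutinib response 10%; share s with an analog change 10% to 30%; chance q that the change itself produces a qualifying fall 20% to 40%. The protocol does not say that analogs lower CgA or 5-HIAA; q rests on its statement about hormonal symptoms.

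Observed rate = 0.10(1 − s) + s[1 − 0.9(1 − q)] = 0.10 + 0.9sq.
- s = 0.10, q = 0.20: 0.10 + 0.018 = 11.8%.
- s = 0.30, q = 0.40: 0.10 + 0.108 = 20.8%.

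If the changes occur at month 3, this applies to the 7.3 definition, which has no time limit. It does not apply to early CgA response, whose value is taken at about that time.

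**4. Illustration for PFS if the patient is not censored.** All inputs are assumed: exponential PFS with median m and λ = ln 2 / m; share s changes analog at month 3; hazard ratio h afterwards. For t > 3, S(t) = (1 − s)exp(−λt) + s·exp(−3λ − λh(t − 3)). Solve S(t) = 0.5.

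| s | h | Shift, m = 6 months | Shift, m = 12 months |
|---|---|---|---|
| 10% | 0.85 | 0.05 | 0.14 |
| 30% | 0.85 | 0.14 | 0.44 |
| 10% | 0.70 | 0.10 | 0.30 |
| 30% | 0.70 | 0.31 | 0.95 |
| 30% | 0.35 | 0.82 | 2.63 |

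Check of the last cell: λ = 0.0578 and t = 14.63 give 0.7 × 0.429 + 0.3 × 0.665 = 0.301 + 0.199 = 0.50. On the 12-month base, one-year PFS moves from 50% to 50.8% (s = 10%, h = 0.70) and to 56.0% (s = 30%, h = 0.35).

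**The case against.** The protocol is not silent. Section 5.3 asks for stable medication, wants the investigator consulted before anything is added, and has changes recorded with a reason. Criterion 6 mentions concurrent analogs only for secretory tumors, which argues against reading 5.3 as open permission. Criterion 7 means that every pNET and every gastrointestinal carcinoid patient has already progressed on, or not tolerated, an analog; only lung and unknown-primary patients can be naive, and their number is not given. The endpoints concerned carry no test or decision rule, and 8.2 calls the correlative results hypothesis-generating.

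Most of this stands, and it limits the size. It does not close the gap. The stability rule yields to medical need, which is just when an analog would be added; criterion 6 governs entry; and recording a change does not tell the analyst what to do with the marker value that follows.

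A reader might infer more than the documents support:
- *That PFS has no analysis rule.* Section 7.3 has one; its trigger is unclear for analogs.
- *That the response-rate result is affected.* Section 1.1 speaks of slower progression, not shrinkage, and 7.2 does not let markers alone define response.
- *That PFS is biased toward ibrutinib under either handling.* Censoring favors ibrutinib only if patients whose analog is changed have a worse outlook than the rest. That is plausible for symptom-driven changes, but the documents do not establish it.
- *That median PFS may be overstated by 2.6 months.* That needs the longest base, the largest share and the strongest hazard ratio together, in a population largely past analog benefit or unable to tolerate it.

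**Conclusion.** The point holds in a limited form. For biochemical response it is a real defect: applied as written, 7.3 and 8.2 credit an analog-driven marker fall to ibrutinib, and for early CgA response this is confined to changes before the three-month assessment. For PFS it is an undefined term in an existing rule, to be settled before results are seen.

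The size cannot be derived from the documents. The illustrative ranges (11.8% to 20.8% observed against a true 10%; 0.05 to 2.63 months on median PFS) rest wholly on assumed shares, timing and effects. Prior progression on, or intolerance of, an analog in gastroenteropancreatic patients makes the upper ends unlikely. Only secondary and exploratory endpoints are affected; the response-rate design and its decision rules are untouched. The change is worth making because it is cheap.

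**What to change.** 1. **Markers.** For marker change and biochemical response (7.3 and 8.2), use only values taken before the first on-study start or dose increase of an analog.
2. **PFS.** State in 7.3 whether such a change is further anti-cancer therapy, and report PFS under the other handling as a sensitivity analysis. Either choice can be defended as the main analysis. Counting an analog start as a PFS event would depart from the plan's own definition and is not needed.
3. **Data and reporting.** Have the CRF capture analog dose and start or change dates: 5.3 asks for the reason and drug name, and the visit schedule for medications at each visit, but neither expressly asks for dose or change dates. Report the number of patients affected in each cohort.
4. **Consistency.** Criterion 6 in 4.4.1 ties concurrent analogs to secretory tumors, while the exemption in 5.3 has no such limit. The two must be reconciled.

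**Cost.** Wording in 7.3 and 8.2, possibly one added CRF field, one extra PFS analysis, and the loss of a few later marker values. Sample size and the response-rate rules do not change.

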5.3.1 Drugs That May Have Their Plasma Concentrations Altered by Ibrutinib

In vitro studies indicated that ibrutinib is not a substrate of P-glycoprotein (P-gp), but is a mild inhibitor (with an IC₅₀ of 2.15 µg/mL). Ibrutinib is not expected to have systemic drug-drug interactions with P-gp substrates. However, it cannot be excluded that ibrutinib could inhibit intestinal P-gp after a therapeutic dose. There is no clinical data available; therefore, co-administration of narrow therapeutic index P-gp substrates (eg, digoxin) with ibrutinib may increase their blood concentration and should be used with caution and monitored closely for toxicity.

5.3.1.1 QT Prolonging Agents

Any medications known to cause QT prolongation should be used with caution; periodic ECG and electrolyte monitoring should be considered.

5.3.1.2 Antiplatelet Agents and Anticoagulants

Warfarin or vitamin K antagonists should not be administered concomitantly with ibrutinib. Supplements such as fish oil and vitamin E preparations should be avoided. Use ibrutinib with caution in subjects requiring other anticoagulants or medications that inhibit platelet function. Subjects with congenital bleeding diathesis have not been studied. Ibrutinib should be held at least 3 to 7 days pre- and post-surgery depending upon the type of surgery and the risk of bleeding (see Section 5.5).

5.4 Interruption or Discontinuation of Treatment

Patients may be removed from study for the following reasons:

- Documented disease progression or symptomatic tumor progression. In the case of symptomatic tumor progression, all efforts should be made to document disease status radiologically prior to removal from study;
- Occurrence of unacceptable toxicity (see table 5-2 regarding dose modifications for toxicity). Patients removed from treatment for intolerable toxicity should still be followed with regular tumor assessments until disease progression or start of a new treatment;
- Patient has been off treatment for >3 weeks;
- The patient chooses to terminate participation in the study;
- At the discretion of the investigator;
- If, at any time, the constraints of this protocol are detrimental to the patient's health and/or the patient no longer wishes to continue protocol therapy, protocol therapy shall be discontinued. In this event the study chairs should be notified, the reasons for discontinuation should be documented, and the patient should be followed as appropriate per study.

